
OBJECTIVE

The objective of this study is to perform a prospective, single-arm clinical evaluation utilizing the Spira™-C 3-D printed titanium interbody device for treatment of degenerative disc disease and spinal stenosis of the cervical spine to evaluate fusion status and patient reported outcomes. The primary objective is fusion status; this will be measured using dynamic (flexion and extension) X-rays and CT scan at 12 months. Secondary objectives include evaluation of patient reported outcomes, VAS score (pain), NDI (neck disability index; pain and function), SF-36 (quality of life), and EAT-10 (dysphagia). Also, radiographs will be evaluated for the occurrence of device-related adverse events or complications, such as revision surgery at the index level, subsidence, migration, and failure or loosening of the interbody device. Neurological motor and sensory evaluations will be followed for improvement or worsening over the course of the study. Data collected from subjects treated with the Spira™-C Interbody Device will be compared to historical data based on literature review of fusion rates and patient reported outcomes of traditional PEEK interbody cages.

DESCRIPTION OF SPIRA™-C OPEN MATRIX CERVICAL INTERBODY DEVICE

The Spira™-C Open Matrix Cervical Interbody Device, manufactured by Camber Spine Technologies, was 510(k) cleared by the FDA on October 17, 2017. The Spira™-C device is a 3-D printed titanium alloy cage designed with open spiral supports to allow for a hollow chamber to facilitate the packing of bone graft to optimize fusion. Spira™-C is indicated for use at one or two contiguous levels from C3-C7 for degenerative disc disease (DDD) with up to grade I spondylolisthesis. It is intended to be used with a supplementary FDA-cleared plate fixation system. Spira™-C must be used with autograft or cancellous or cortico-cancellous allograft.

METHODOLOGY

Study Design

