This is a post-market, single-arm, prospective clinical study to evaluate fusion status and patient reported outcomes using the Spira-C titanium interbody cage for degenerative disc disease where single-level ACDF surgery is indicated. The treatment group will consist of 40 subjects treated with the Spira™-C Interbody Device at one level. Patients with a diagnosis of cervical degenerative disc disease and/or spinal stenosis, radiculopathy or myelopathy and planning to undergo a 1-level ACDF surgery between C3-C7 will be screened. If the subject meets all of the inclusion criteria and none of the exclusion criteria, the patient will be approached regarding study participation by the surgeon or study coordinator. If the subject wishes to participate, the study coordinator will initiate the consent process. Once the consent process has been completed and the subject has signed an IRB approved informed consent form the medical history, cervical spine examination (motor/sensory), and baseline subject questionnaires (VAS, NDI, SF-36, and EAT-10) will be collected. Once the ACDF surgery has taken place as planned; data will be regarding the surgery performed, operative time, bone graft used, plate and screw fixation system used,

length of stay, and adverse events or complications related to the procedure, device, or cervical spine.

Subjects will be followed up postoperatively at 6-weeks, 3-months, 6-months, and 12-months as per standard of care, at the private practice or clinic. During these visits, subjects will complete the questionnaires, cervical spine (motor/sensory) examination completed by the investigator, and cervical spine x-rays done per standard of care. Adverse events related to the device and/or procedure and/or cervical spine will be assessed at each visit.

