in non-union or pseudoarthrosis and/or clinically significant neurological symptomology will be considered a device failure and reported as an adverse event.

- No new or worsening neurological (motor and sensory of the cervical spine) deficit as compared to baseline through 12-months.

SUBJECT SCREENING AND ENROLLMENT

Patients scheduled to undergo a primary single-level ACDF surgery between C3-C7 will be approached about potential study participation. If the patient wishes to proceed with study participation, the study coordinator will perform the informed consent process. After the consent process has been completed and study details have been discussed, the subject will be further screened for eligibility and given the subject questionnaires to complete.

Screen Failures

If the subject does not meet all inclusion criteria or meets one of the exclusion criteria after signing consent, then the subject will be considered a screen failure and therefore, not enrolled into the study. The subject will also be considered a screen failure and not enrolled in the study if there is a change in surgical treatment based on the surgeon's observations and best practice intraoperatively.

Withdrawals

A subject who withdraws consent prior to study completion will be removed from the study and no longer followed. The surgery, instrumentation, and bone grafts are FDA approved and cleared and considered standard of care. The subjects may follow-up as needed and per standard of care at their own discretion if they decide to no longer participate in the study. The reasons for voluntary withdrawal or discontinuation of study subjects will be documented. If during the course of the clinical study, a study subject is non-responsive to attempts to schedule follow-up visits, communication methods such as phone calls, emails, mail, or other means as appropriate in an attempt schedule an appointment or determine if the subject has moved, died, or otherwise become lost to follow-up.

Study Synopsis

Sponsor	Camber Spine Technologies [name]
Protocol Version	Version 1.2 Date: 11.01.18
Study Title	A PROSPECTIVE CLINICAL PILOT STUDY OF FUSION RATES USING SPIRA™-C TITANIUM 3D PRINTED INTERBODY DEVICE FOR ANTERIOR CERVICAL DISCECTOMY AND FUSION (ACDF)
Site/ PI	Beaumont Health – Royal Oak (William Beaumont Hospital) Principal Investigator: [name]

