	
 8. History of osteoporosis, osteopenia, or osteomalacia that would contraindicate spinal surgery 9. Psychological or physical condition in the opinion of the investigator that would interfere with study participation, including completion of patient reported outcomes 10. History of neurological condition in the opinion of the investigator that may affect cervical spine function and pain assessments 11. Subjects with a history of cancer must be disease free for at least 3 years; with the exception of squamous cell skin carcinoma 12. Pregnant, or plans on becoming pregnant 13. History of allergy to titanium

Study Schedule of Events
	
All subjects who sign an IRB approved consent form are considered in active screening to determine eligibility. Once a subject is consented, the following visits will take place:
 
Baseline Visit:
 
 • Medical history • Cervical Spine Exam • Demographics • VAS, NDI, SF-36, EAT 10 questionnaires • Cervical spine x-rays AP/lateral, flexion/extension or as done per standard of care 
Surgical Visit (≤ 60 days of baseline visit):
 
 • Surgery performed • Amount of Bone Graft, both local bone autograft/allograft used • Cervical plate and screw fixation system used • Adverse Events/Complications 
6-week Visit (± 2 weeks):
 
 • VAS, NDI, SF-36, EAT 10 • Cervical Spine Exam • Cervical AP/Lateral x-rays • Adverse Events 
3-month Visit (± 3 weeks):
 
 • VAS, NDI, SF-36, EAT 10, patient satisfaction questionnaires • Cervical Spine Exam • Cervical AP/Lateral and flexion/extension x-rays • Adverse Events 
6-month Visit (± 1 month):
 
 • VAS, NDI, SF-36, EAT 10 • Cervical Spine Exam • Cervical AP/Lateral and flexion/extension x-rays • Adverse Events

	
12-month Visit (\pm 2 months):
 
• VAS, NDI, SF-36, EAT 10• Cervical Spine Exam• Cervical AP/Lateral and flexion/extension x-rays• CT scan of the cervical spine without contrast• Adverse Events
--	---

REFERENCES

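### The Surgical Visit is the only scheduled visit without a motor/sensory exam, so an early deficit that resolves before day 28 to 56 and goes unrecorded would count as a success on the neurological endpoint

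*Combined protocol and SAP*

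**What the plan says.** The endpoint, in Outcomes (Secondary Endpoints) and again in the synopsis, is "No new or worsening neurological (motor and sensory of the cervical spine) deficit as compared to baseline through 12-months". The Objective section says "Neurological motor and sensory evaluations will be followed for improvement or worsening over the course of the study".

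Study Design places the first exam after consent and before surgery: "cervical spine examination (motor/sensory), and baseline subject questionnaires (VAS, NDI, SF-36, and EAT-10) will be collected". For the operation it lists operative data together with "length of stay, and adverse events or complications related to the procedure, device, or cervical spine", and no exam. It then states "Subjects will be followed up postoperatively at 6-weeks, 3-months, 6-months, and 12-months as per standard of care", and at those visits there is a "cervical spine (motor/sensory) examination completed by the investigator".

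The Study Schedule of Events in the synopsis agrees. A Cervical Spine Exam is listed at the baseline visit and at 6 weeks, 3, 6 and 12 months. The entry headed "Surgical Visit (≤ 60 days of baseline visit" lists the surgery, graft, fixation system and adverse events or complications. The next entry is "6-week Visit (± 2 weeks". Neither section mentions a discharge or early post-operative exam.

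**The concern.** The endpoint claims absence of a new or worse deficit over the whole period, but the schedule makes no structured comparison with baseline at the time when a deficit caused by the operation would first appear. Until the 6-week visit, detection depends on someone noticing the deficit and recording it as an adverse event.

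The error has one direction: an unseen transient deficit leaves the subject classed as a success. In a 40-subject single-arm study, a single case separates a report of no deficits from a non-zero rate. What is at stake is the accuracy of one descriptive secondary safety rate.

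**Working it through.** **1. The plan's own precision figures.** Statistical Analysis gives 95% Wilson interval widths for n = 40 of 0.274 at a proportion of 0.70 and 0.088 at 1.00. The interval without continuity correction, with z = 1.96, is

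[p + z²/(2n) ± z·√(p(1−p)/n + z²/(4n²))] / (1 + z²/n).

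- p = 0.70: 0.546 to 0.819, width 0.2736.
- p = 1.00: 0.912 to 1.000, width 0.0876.

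Both stated figures are reproduced. They concern the fusion rate; the same method is used in step 5.

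**2. Exams by visit (synopsis schedule).**

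| Visit | Cervical Spine Exam | Adverse events |
|---|---|---|
| Baseline | yes | not listed |
| Surgical | no | yes |
| 6 weeks | yes | yes |
| 3 months | yes | yes |
| 6 months | yes | yes |
| 12 months | yes | yes |

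The Study Design narrative gives the same pattern, so the omission is not a product of how the table was extracted.

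**3. Post-operative time without a scheduled exam.**
- Earliest: (6 − 2) × 7 = 28 days.
- On target: 6 × 7 = 42 days.
- Latest: (6 + 2) × 7 = 56 days.

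**4. Conditions for a missed case.** All three must hold: the deficit appears after surgery, it has resolved by the first exam, and it was not noticed and recorded as an adverse event at surgery or at the 6-week visit.

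**5. Illustration of size (assumed rates).** The documents give no early deficit rate. Suppose all 40 subjects are assessed, and one or two have a transient deficit that is not captured in any way:

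| Result | Rate | Wilson 95% interval |
|---|---|---|
| Reported 40/40 | 100% | 91.2% to 100% |
| True 39/40 | 97.5% | 87.1% to 99.6% |
| True 38/40 | 95.0% | 83.5% to 98.6% |

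Over a wider assumed range, let r be the early deficit rate (2.5% to 10%) and f the fraction resolved before the first exam (25% to 75%), with none captured another way.
- Expected misclassified subjects, 40·r·f: from 40 × 0.025 × 0.25 = 0.25 to 40 × 0.10 × 0.75 = 3.
- Chance of at least one, 1 − (1 − r·f)^40: from 1 − (1 − 0.00625)^40 = 22% to 1 − (1 − 0.075)^40 = 96%.

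The width of that range shows that the size cannot be settled from the documents. Any capture through adverse events lowers these figures.

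**The case against.** **Every between-visit interval lacks an exam.** A reader might infer that the early weeks are the only unexamined part of follow-up. The schedule does not support that. With windows, 3 to 6 months can reach about 143 days, and 6 to 12 months about 9 months (month 5 to month 14). The 28 to 56 days after surgery are among the shortest intervals. This stands. The narrower point survives: surgery is the only scheduled visit with no exam, and it is where an operative deficit begins.

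**The interval is not 116 days.** It is tempting to add the 60 days allowed before surgery to the 56 days after it. A deficit that appears after surgery cannot arise in the first 60, so the relevant figure is 28 to 56 days. The age of the baseline exam is a separate matter.

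**Adverse events are recorded.** At surgery and at each visit, events related to the procedure, device or cervical spine are captured, and a new motor or sensory deficit can fall within that scope. This narrows the gap without closing it, because such recording is not a scheduled comparison with baseline.

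**A recorded deficit may already count.** A reader might infer that a deficit attributed to the procedure could be recorded and enter neither endpoint, since the adverse-event endpoint is limited to device-related events. But the neurological endpoint is not restricted to findings at scheduled exams. On its plain wording, a documented new deficit fails it. No text links the two records explicitly, so a sentence saying so is a clarification, not the repair of an error.

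**Little depends on the result.** The endpoint is secondary, with no hypothesis or threshold. The historical comparison covers fusion and patient-reported outcomes, not neurological status. This stands and limits the weight of the point.

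**Conclusion.** The point holds as an inexpensive improvement to the measurement of a secondary endpoint. The endpoint covers the whole period through 12 months, yet the one visit at which an operative deficit would first show has no structured exam, and the next exam is 28 to 56 days later. A deficit meeting all three conditions in step 4 would be counted as a success, so the rate could be biased upward.

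A reader might go further and infer that the rate is biased. The documents do not support that: they give no early deficit rate and no means of judging how many cases adverse-event recording would catch. The 39/40 and 38/40 figures rest on assumed counts, full follow-up of 40 subjects and no other capture. A deficit persisting to week 4 to 8 would be found. The primary fusion analysis, the sample size and its precision statement are unaffected.

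**What to change.** 1. In the synopsis schedule, add Cervical Spine Exam to the Surgical Visit, done once after surgery and before discharge on the form used at the other visits. Make the matching change in Study Design.
2. As an accompanying clarification, state with the endpoint, in both Outcomes and the synopsis, that any new or worse motor or sensory deficit recorded after surgery fails it, including one recorded as an adverse event. Report resolved and persistent deficits separately.

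**Cost.** Change 1 is one short exam and one form per subject, up to 40 in all, by the existing investigators at a visit already scheduled. Change 2 is one sentence and uses data already collected. The neurological rate may come out slightly less favourable; the separate reporting shows how much of that is transient. The time from discharge to the 6-week visit would still rely on adverse-event recording. Both changes concern measurement only and leave treatment, eligibility and sample size as they are.
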